7.2 Serious adverse events

7.2.1 Definition of SAE

An SAE is defined as any adverse event (appearance of (or worsening of any pre-existing) undesirable sign(s), symptom(s) or medical condition(s) which meets any one of the following criteria:

- is fatal or life-threatening
- results in persistent or significant disability/incapacity
- constitutes a congenital anomaly/birth defect
- requires inpatient hospitalization or prolongation of existing hospitalization, unless hospitalization is for:
 - routine treatment or monitoring of the studied indication, not associated with any deterioration in condition (specify what this includes)
 - elective or pre-planned treatment for a pre-existing condition that is unrelated to the indication under study and has not worsened since signing the informed consent
 - treatment on an emergency outpatient basis for an event not fulfilling any of the definitions of a SAE given above and not resulting in hospital admission
 - social reasons and respite care in the absence of any deterioration in the patient's general condition
- is medically significant, i.e. defined as an event that jeopardizes the patient or may require medical or surgical intervention.

All malignant neoplasms will be assessed as serious under "medically significant" if other seriousness criteria are not met.

Life-threatening in the context of a SAE refers to a reaction in which the patient was at risk of death at the time of the reaction; it does not refer to a reaction that hypothetically might have caused death if more severe (see Annex IV, ICH-E2D Guideline).

Medical and scientific judgment should be exercised in deciding whether other situations should be considered serious reactions, such as important medical events that might not be immediately life threatening or result in death or hospitalization but might jeopardize the patient or might require intervention to prevent one of the other outcomes listed above. Examples of such events are intensive treatment in an emergency room or at home for allergic bronchospasm, blood dyscrasias or convulsions that do not result in hospitalization or development of dependency or abuse (see Annex IV, ICH-E2D Guideline).

Any suspected transmission via a medicinal product of an infectious agent is also considered a serious adverse reaction.

All AEs (serious and non-serious) are captured on the CRF, SAEs also require individual reporting to Novartis DS&E as per [Section 7.2.2](#).

7.2.2 SAE reporting

To ensure subject safety, every SAE, regardless of causality, occurring after the subject has provided informed consent and until 84 days after the last dose of study medication, must be reported to Novartis within 24 hours of learning of its occurrence. Any SAEs experienced after the 84-day period should only be reported to Novartis if the investigator suspects a causal relationship to study treatment.

Recurrent episodes, complications, or progression of the initial SAE must be reported as follow-up to the original episode, regardless of when the event occurs. This report must be submitted within 24 hours of the investigator receiving the follow-up information. An SAE that is considered completely unrelated to a previously reported one should be reported separately as a new event.

Information about all SAEs (either initial or follow up information) is collected and recorded on the paper Serious Adverse Event Report Form. The investigator must assess the relationship of each SAE to study treatment, complete the SAE Report Form in English, and send the completed, signed form by fax within 24 hours after awareness of the SAE to the local Novartis Drug Safety and Epidemiology Department. The telephone and fax number of the contact persons in the local department of Drug Safety and Epidemiology, specific to the site, are listed in the investigator folder provided to each site. The original copy of the SAE Report Form and the fax confirmation sheet must be kept with the subject's source documentation at the study site. Follow-up information should be provided using a new paper SAE Report Form stating that this is a follow-up to a previously reported SAE.

Follow-up information provided should describe whether the event has resolved or continues, if and how it was treated, whether the treatment code was broken or not and whether the subject continued or withdrew from study participation. Each re-occurrence, complication, or progression of the original event should be reported as a follow-up to that event regardless of when it occurs.

If the SAE is not previously documented in the Investigator's Brochure or Package Insert (new occurrence) and is thought to be related to the study treatment, a Drug Safety and Epidemiology Department associate may urgently require further information from the investigator for Health Authority reporting. Novartis may need to issue an Investigator Notification (IN) to inform all investigators involved in any study with the same study treatment that this SAE has been reported. Suspected Unexpected Serious Adverse Reactions (SUSARs) will be collected and reported to relevant ethics committees in accordance with regulatory requirements.

7.3 Liver safety monitoring

There has been no safety signal for liver toxicity with secukinumab to date in over 6535 patients exposed and from a mechanism of action standpoint there is no effect of blocking IL-17A on the liver. Liver function tests will be obtained at regular intervals but special measures for liver safety monitoring are not planned.

7.4 Pregnancy reporting

To ensure patient safety, each pregnancy occurring while the patient is on study treatment must be reported to Novartis within 24 hours of learning of its occurrence. The pregnancy should be followed up to determine outcome, including spontaneous or voluntary termination, details of the birth, and the presence or absence of any birth defects, congenital abnormalities, or maternal and/or newborn complications.

Pregnancy should be recorded on the Pharmacovigilance Pregnancy Form and reported by the investigator to the local Novartis Drug Safety and Epidemiology Department. Pregnancy follow-up should be recorded on the same form and should include an assessment of the possible relationship to the study treatment.

Any SAE experienced during the pregnancy and unrelated to the pregnancy must be reported on a SAE form.

8 Data review and database management

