5.5.4 Instructions for prescribing and taking study treatment

All study treatment (150 mg secukinumab, or placebo) will be self-administered subcutaneously throughout the study after the study assessments for the visit have been completed. Site staff will administer the injection only to those patients who are not able to self-administer the PFS injection. Detailed instructions on the self-administration of the study treatment will be described in the Instructions For Use (IFU) and provided to each subject.

The first study treatment administration will occur at the randomization visit (BL) **after** inclusion/exclusion criteria have been confirmed, all study scheduled assessments have been performed and the scheduled blood samples have been drawn.

The subject will be instructed by the site staff, utilizing the IFU, on how to self-inject via PFS. Patients will be asked to raise any questions, if they have any, and then to proceed with self-injection. Self-injection will take place under the supervision of a site staff member. At the Week 1 and subsequent visits, patients will be asked to refer to the IFU and to proceed with self-injection of the study drug.

Study treatment will be administered weekly following the BL dose (Weeks 1, 2, 3, & 4) and every 4 weeks thereafter (Week 8 until Week 48)

All dates and times of injections self-administered by the subject during the study must be recorded on the Dosage Administration Record eCRF. Immediately before dispensing the drug package to the subject, the investigator staff will detach the outer part of the label from the packaging and affix it to the source document (Drug Label Form) for that subject's unique subject number.

The investigator should promote compliance by instructing the subject to attend the study visits as scheduled and by stating that compliance is necessary for the subject's safety and the validity of the study. The subject should be instructed to contact the investigator if he/she is unable for any reason to attend a study visit as scheduled or if he/she is unable for any reason to take the study treatment as prescribed.

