5.5.13 Study completion and post-study treatment

A subject's individual study participation is completed once Visit 19/Week 52 Treatment Period has been completed. Any SAEs that occur in the following 84 days (12 weeks) after the dose of study drug must be reported. The investigator will also follow any AEs for which there is no outcome that can be reported at the final study visit.

The study as a whole will be completed once all randomized patients have completed the study as per the protocol and the clinical database has been locked. Recruitment into the study will be terminated by the sponsor once the targeted number of randomized patients has been met or is foreseen to be met with the patients already in screening. Patients who have been screened and have a screening visit recorded in the IRT system at the time that the planned

enrollment number is met will be allowed to enter the trial and to be randomized if they are eligible.

Upon completion of their study participation, patients will return to individual treatment, as determined by their treating physician.

The investigator must provide follow-up medical care for all patients who are prematurely withdrawn from the study, or must refer them for appropriate ongoing care.

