For patients who discontinue study treatment prematurely for any reason before the end of **Treatment Period 1**, (Visit 10/Week 16 EOT1) must be performed approximately four weeks after the last dose of study treatment (secukinumab 300 mg, secukinumab 150 mg or placebo). Patients should also be contacted via telephone, 84 days (12 weeks) after last dose of study drug, to inquire about any AE/SAEs that occurred during this period.

For patients who discontinue study treatment prematurely for any reason before the end of **Treatment Period 2**, (Visit 19/ Last visit EOT2) must be performed approximately four weeks after the last dose of study treatment (300 mg or 150 mg s.c. secukinumab). Patients should also be contacted via telephone, 84 days (12 weeks) after last dose of study drug, to inquire about any AE/SAEs that occurred during this period.

If patients refuse to return for these assessments or are unable to do so, every effort should be made to contact them or a knowledgeable informant by telephone to determine the reason.

At a minimum, patients will be contacted for safety evaluations during the 84 days (12 weeks) following the last study visit or following the last administration of study treatment (whichever is later), including a final contact at the 84-day point. Documentation of attempts to contact the subject should be recorded in the source documentation.

AE/SAE information obtained as a result of these calls must be recorded in the eCRF.

Unscheduled visits

Patients may be seen at any time for an unscheduled visit, e.g., if they experience deterioration or AEs that in the opinion of the investigator/qualified site staff need intervention or repeat laboratory testing. The assessment(s) performed at an unscheduled visit must include at minimum: an assessment of concomitant medication and procedures/significant non-drug therapies, vital signs, and an AE/SAE assessment. Any additional assessments performed are at the investigator/qualified site staff's discretion. During an unscheduled visit, study treatment will not be administered.

Table 6-1 Assessment schedule

Period	SCR ¹		Treatment Period 1								Treatment Period 2									Unscheduled Visit	
Week	-8 to BL		BL	1	2	3	4	8	12	16/EOT	20	24	28	32	36	40	44	48	52/EOT		Day 84 Safety Follow-up ⁴
Visit No	1	2	3	4	5	6	7	8	9	10	11	12	13	14	15	16	17	18	19		
Visit Window (days) ²				+/-2	+/-2	+/-2	+/-2	+/-2	+/-2	+/-2	+/-7	+/-7	+/-7	+/-7	+/-7	+/-7	+/-7	+/-7	+/-7		
Assessments																					

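### Pregnancies that begin after treatment ends, but within the 84-day safety window, do not have to be reported or followed to outcome

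*Protocol*

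**What the plan says.** Protocol 7.4 is the only pregnancy-reporting rule in the documents: "each pregnancy occurring while the patient is on study treatment must be reported to Novartis within 24 hours of learning of its occurrence". It then asks for follow-up to outcome, including birth defects and maternal or newborn complications. It gives no period after treatment.

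Protocol 7.2.2 sets a longer period for SAEs. Every SAE from consent "until 84 days after the last dose of study medication, must be reported to Novartis within 24 hours of learning of its occurrence". Beyond that point, "Any SAEs experienced after the 84-day period should only be reported to Novartis if the investigator suspects a causal relationship to study treatment".

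Protocol Section 6, under premature discontinuation, has patients "contacted for safety evaluations during the 84 days (12 weeks) following the last study visit" or the last administration of study treatment, whichever is later. The purpose of the telephone call is "to inquire about any AE/SAEs that occurred during this period". Table 6-1 has a Day 84 safety follow-up column, but the last urine pregnancy test in that table is at Week 52.

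Other passages touch on pregnancy without adding a reporting duty. Protocol 5.5.9 makes it a reason to stop treatment. Protocol 6.5.6 covers testing and discontinuation. Protocol 4.2 (exclusion 11) and 10.2 cover contraception. SAP 2.8.3 plans summaries and listings of urine test results.

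**The concern.** The sponsor has set 84 days after the last dose as the time over which it wants to hear of any serious event, whatever its cause. Pregnancy reporting is tied instead to being on treatment. Pregnancy is not itself an SAE criterion in Protocol 7.2.1, so the SAE rule does not bring it in.

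What is at stake is safety information. Protocol 10.2 has women told that treatment may carry unknown risks to a fetus. Outcomes of pregnancies that begin soon after the last dose bear on that question. If the follow-up in 7.4 is not triggered when the pregnancy becomes known, the outcome may not be recoverable later. The primary analysis, power and type I error are not involved.

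**Working it through.** The plan gives no figure of its own to reproduce. The check compares reporting windows and counts days on the study calendar.

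**Inputs**
- Last scheduled dose: Week 48 (Protocol 5.5.4), which is Day 337 (SAP Table 2-1).
- End of participation: Week 52 (Protocol 5.5.13), which is Day 365 (SAP Table 2-1).
- SAE reporting: to 84 days after the last dose (Protocol 7.2.2).
- End of treatment: the protocol does not define the phrase used in 7.4. SAP 2.1.1 supports two readings. It puts the treatment end date at the last non-zero dose, but it also describes a treatment phase of 52 weeks.

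**Completers**
- End of SAE window: 337 + 84 = Day 421, which is Week 48 + 12 = Week 60.
- Uncovered if treatment ends at the last dose: 421 − 337 = 84 days.
- Uncovered if treatment ends at Week 52: 421 − 365 = 56 days.
- As calendar time this is 12/60 = 20% or 8/60 = 13% of the weeks from first dose to Week 60. It is not a share of pregnancies.

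**Early stoppers**
- The final visit falls about four weeks after the last dose (Protocol Section 6). The gap is 84 days counted from the last dose, or about 84 − 28 = 56 days counted from that visit.

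**Last safety contact**
- If the rule of taking the later of last visit and last dose applies to completers, contact runs to 365 + 84 = Day 449, which is 449 − 337 = 112 days after the last dose. The sentence stands under premature discontinuation, so its reach to completers is a matter of reading. On either reading, contact extends at least to the end of the SAE window.

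**What each rule requires**

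| Situation | Pregnancy report and outcome follow-up (7.4) | SAE report (7.2.2) |
|---|---|---|
| Begins on treatment, found on treatment | Required | Only if a serious event occurs |
| Begins on treatment, found afterwards | Required: 7.4 turns on when the pregnancy occurs, and the 24 hours run from learning of it | Only if a serious event occurs |
| Begins after treatment ends, within 84 days of last dose | Not required | Only if a serious event occurs; after 84 days only if causality is suspected |

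The third row is the gap. A birth defect is an SAE under 7.2.1. But a pregnancy that begins after the last dose would not reach term within 84 days, so a defect found at birth would be reportable only on suspected causality. The investigator would also have to hear of it without the follow-up that 7.4 provides.

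**The case against.** The best answer is that nothing in the documents contradicts itself. No passage says the pregnancy and SAE windows must agree, and the protocol never describes the 84 days as a period of fetal exposure. That stands: this is a design choice that could be improved. The documents also give no data on how long the drug persists, so harm from exposure after the last dose is not shown.

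There are partial safeguards. A urine pregnancy test is scheduled at Week 52, four weeks after the last scheduled dose. Serious maternal events are reportable for 84 days. Protocol 7.1 asks patients to report later events that might be related to treatment, and sends those that are serious to the sponsor. These catch some serious outcomes. They do not create a duty to report or follow a post-treatment pregnancy as such.

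A reader might infer more than the text supports:
- *That any pregnancy found in the 84 days escapes reporting.* It does not. A pregnancy that began on treatment is covered whenever it is discovered.
- *That 7.4 expressly forbids or excludes later reports.* It does not use the word only. The limit follows from the absence of any other pregnancy-reporting rule, and a site could report voluntarily.
- *That such pregnancies will be missed.* The supportable statement is that reporting and follow-up are not required.

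**Conclusion.** The gap is real and narrow. It concerns pregnancies that begin after treatment ends and within 84 days of the last dose. For a completer it lasts 84 days if treatment ends at the Week 48 dose, or 56 days if the SAP's 52-week treatment phase is used, so it exists on either reading.

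The conclusion rests on two things: 7.4 being the only pregnancy-reporting rule in the documents, and the sponsor's 84-day SAE window being the natural period to match. Expected numbers are small; the documents give no basis for estimating them. No efficacy result, power figure or error rate depends on the point. It is worth changing because the change is cheap and an unrecorded outcome may be hard to recover.

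**What to change.** Reconcile Protocol 7.4 with 7.2.2 by extending the end of the pregnancy-reporting window to 84 days after the last dose. Counting from the last dose also removes the need to interpret when treatment ends. Keep the trigger as the time the pregnancy begins, so that one conceived in the window but recognised later is still reported and followed. Only the end of the window changes. The SAE window starts at consent, and its start need not be copied.

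Add a pregnancy question for women of child-bearing potential at the Day 84 safety contact. A pregnancy that begins late in the window may not yet be known at that call, so the question helps but does not replace the reporting duty.

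The cost is a written amendment with the approvals listed in Protocol 11.1 (sponsor, IRB/IEC, and health authorities where required), one added question, and a few extra pregnancy forms with follow-up. No visit, test or statistical analysis is added.

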8.1 Site monitoring

Before study initiation, at a site initiation visit or at an investigator's meeting, a Novartis representative will review the protocol and CRFs with the investigators and their staff. During the study, Novartis employs several methods of ensuring protocol and GCP compliance and the quality/integrity of the sites' data. The field monitor will visit the site to check the completeness of patient records, the accuracy of entries on the (e)CRFs, the adherence to the protocol and to Good Clinical Practice, the progress of enrollment, and to ensure that study treatment is being stored, dispensed, and accounted for according to specifications. Key study personnel must be available to assist the field monitor during these visits.

The investigator must maintain source documents for each patient in the study, consisting of case and visit notes (hospital or clinic medical records) containing demographic and medical information, laboratory data, electrocardiograms, and the results of any other tests or assessments. All information on CRFs must be traceable to these source documents in the patient's file. The investigator must also keep the original informed consent form signed by the patient (a signed copy is given to the patient).

The investigator must give the monitor access to all relevant source documents to confirm their consistency with the CRF entries. Novartis monitoring standards require full verification for the presence of informed consent, adherence to the inclusion/exclusion criteria, documentation of SAEs, and of data that will be used for all primary variables. Additional checks of the consistency of the source data with the CRFs are performed according to the study-specific monitoring plan. No information in source documents about the identity of the patients will be disclosed.

8.2 Data collection

Designated investigator staff will enter the data required by the protocol into the Electronic Case Report Forms using fully validated software that conforms to US CFR 21Part 11

requirements. Designated investigator site staff will not be given access to the EDC system until they have been trained.

Automatic validation programs check for data discrepancies and, by generating appropriate error messages, allow the data to be confirmed or corrected before transfer of the data to the CRO working on behalf of Novartis. The Investigator must certify that the data entered into the Electronic Case Report Forms are complete and accurate. After database lock, the investigator will receive copies of the patient data for archiving at the investigational site.

8.3 Database management and quality control

A CRO working on behalf of Novartis will review the data entered into the eCRFs by investigational staff for completeness and accuracy and instruct the site personnel to make any required corrections or additions. Queries are sent to the investigational site using an electronic data query. Designated investigator site staff is required to respond to the query and confirm or correct the data. Randomization codes and data about all study drug(s) assigned to the subject will be tracked using an Interactive Response Technology (IRT). The system will be supplied by a vendor, who will also manage the IRT database. The database will be sent electronically to Novartis (or a designated CRO). Each occurrence of a code break via IRT will be reported to the clinical team and study monitor. The code break functionality will remain available until study completion or upon request of Novartis.

Concomitant medications entered into the database will be coded using the WHO Drug Reference List, which employs the Anatomical Therapeutic Chemical classification system. Concomitant procedures, non-drug therapies and adverse events will be coded using the Medical dictionary for regulatory activities (MedDRA) terminology.

Laboratory samples will be processed centrally and the results will be sent electronically to a designated CRO.

PRO questionnaires will be completed by the subject on an electronic tablet, and the data transmitted into the eCRF by investigator site staff.

The occurrence of relevant protocol deviations will be determined. After these actions have been completed and the database has been declared to be complete and accurate, it will be locked and the treatment codes will be unblinded and made available for data analysis. Any changes to the database after that time can only be made after written agreement by Novartis management.

